3.8. Definitions and Derived Variables

[figure not shown]
3.8.1. Study Period Definitions

The study duration for each subject is divided into 3 periods

1. **Screening Period (Visit 1):** The duration from signing informed consent until before receiving the first dose of study drug will be described as the screening period. **The last measurement taken prior to receiving the first dose of study drug (saline injection) is the Baseline measurement. Hence, Baseline measure could be either a scheduled assessment or an unscheduled assessment.**
2. **Treatment period (Visit 2):** Study day 1 (procedure day) is the treatment period. Although the actual date/time for some PK samples may occur on study day 2 or day 3, all PK analysis will be labelled as treatment period because PK period starts on Study Day 1.
3. **Post treatment follow-up period (Visit 3):** this period starts the day after procedure through end of study. **Subjects who completed Visit 3 final follow-up are considered complete the study.**

A study scheme is provided in [Figure 1](#).

Figure 1: Study Scheme

- Subjects who have an onsite visit between Days 7 and 27 may have safety follow-up procedures completed at that time

3.8.2. IC Treatment Responders

A responder (Yes/No) variable will be derived for each subject by comparing the conspicuity score following IC treatment vs the conspicuity score after saline treatment. When there is ≥ 1 point improvement (IC – Saline) in the conspicuity score and the conspicuity score following the IC treatment is (3, 4, or 5) for a subject, this subject is considered a responder of the IC treatment. The responder assessment will be performed for each ureter separately.

3.8.3. Time to Visualization (TTV) of Blue Color in the Ureteral Jets After IC Administration

Each randomized subject is expected to receive 1 dose of saline and 1 dose of IC; time of each injection, including start time and completion time, will be recorded as HHMMSS (hour, minute, and second). **TTV event is assessed only after IC treatment within 10 minutes after the injection start.** Time when this event occurred after IC injection will be captured as HHMMSS. Therefore, TTV following each injection will be derived as follows.

TTV (minutes) = (time when adequate visualization occurs - start time of injection) / 60

If the adequate visualization of blue color in the ureter jet flow at an ureteral orifice following IC injection for a subject did not occur for any reason, this subject will be censored for this analysis. The censored time will be set to 10 minutes.

TTV will be derived for each subject following IC injection for each ureter separately.

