The study will enroll approximately 116 subjects from approximately 10 – 20 study centers in the United States. Subjects scheduled for urological or gynecological surgical procedures, age 18 to 85 years inclusive, will be screened for participation. Screening will occur within 30 days before study drug administration (Day of Surgery). After signing the informed consent, medical history, physical examination, baseline laboratory testing, pregnancy testing, 12-lead ECG, and vital sign measurements will be completed during the screening visit. Any procedure done for the purpose of the surgery before the date of signing the informed consent may be used as long as it was within 30 days of the scheduled surgery date.

On the day of surgery (Day 1) the subject will be evaluated for eligibility for randomization. Eligible subjects will be randomized to receive a dose of either IC high dose (5 mL) or IC low dose (2.5 mL). Each randomized subject will serve as his/her own control by receiving a dose of normal saline prior to receiving the randomized IC dose. The surgeon will be blinded to the IC dose a subject receives. Time of injection of saline and IC will be captured.

To evaluate the efficacy outcomes, each subject will first be injected intravenously with 5 mL 0.9% saline. The ureteral orifices/flow will be observed and video recorded for 10 mins. The time period that will be captured on video is from injection to 10 minutes post injection. If both ureters cannot be visualized simultaneously, then alternating 15-30 second images of each ureter or ureteral orifice will be obtained. The process will be repeated in the same patient for the IC dose. Hence, each subject will have 2 videos and each will be about 10 minutes in length.

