2.1. Study Endpoints

2.1.1. Efficacy Endpoints

The **primary** efficacy endpoint is conspicuity score after each treatment provided by the central readers:

- 1 = No jet observed
- 2 = Weak jet, little color contrast
- 3 = Color contrast or significant jet flow
- 4 = Strong jet flow with good color contrast
- 5 = Strong jet flow with striking contrast in color

The **secondary** efficacy endpoints include:

1. Proportion of physicians who agree that compared to saline, IC treatment improves visualization as an aid for the assessment of ureteral patency
2. To determine proportion of IC treatment responders per the blinded central reviewers' assessment. A subject is a responder to the IC treatment when there is ≥ 1 point difference in the conspicuity scores between the IC and saline treatment (IC – Saline ≥ 1) and the conspicuity score following the IC treatment is (3, 4, or 5). The responder criteria will be assessed separately for each ureter for each subject.
3. Time (minutes) from start of drug administration to visualization (TTV) of the blue color in the ureteral jets flow after IC administration

Other efficacy endpoints will include:

1. Conspicuity scores assessed by the surgeons
2. Concordance of the Conspicuity scores between the surgeons' assessments and the blinded central reviewers' assessments.

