3.8.3.1. Missing Data Imputation Rules for TTV

In order to calculate TTV, the injection start time and time when blue color is adequate visualized in the ureter jet flow must be present. Although the clinical team will make the best effort to eliminate missing or partial time, mistakes could occur. The following rules will be implemented should a subject had missing or partial injection time or time when blue color in the ureter jet flow is adequately visualized.

1. When the injection start time is missing or partial

- 1) If injection start time is missing but the completion time is present, the missing start time will be set to be the same as the injection completion, and vice versa.
- 2) If the hour and minutes are non-missing but the seconds are missing for injection start time, the first second (01) will be assigned to the injection time.
- 3) Otherwise the median elapsed time (defined as time between surgery start time and injection start time) in the study across all subjects who did not have missing data will be used to impute the missing time. That is, the missing injection start time will be set as (Surgery start time + median elapsed time).

The rules will be implemented based on this order.

2. When event occurred but the time is missing or partial

A subject is considered to have had this event when the conspicuity score is 4 or higher per central reader score for this ureter. When a subject has this event but the time when the event occurred is missing, the following rules will be applied.

- 1) If the time is partial (i.e., only the seconds are missing), the first second (01) will be assigned.
- 2) If the time is missing, the subject will not be censored for this endpoint. The missing time, however, will be assigned to 10 minutes after the injection start time.
- 3) This event will be considered as an important protocol deviation. The subject will be excluded from the efficacy PP analysis set. A sensitivity analysis may be performed for the TTV endpoint based on the efficacy PP analysis set.

If a subject had issue(s) with a ureter initially this subject will be censored for this analysis regardless if the issue(s) is or is not fixed during the procedure.

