response. The model estimates the cumulative logits of better outcome (conspicuity=5) to the poor outcome (conspicuity=1). Since it is expected that the interaction effect will not be statistically significant ($p > 0.10$), a reduced model (**Model 2**) will also be used in which the interaction effect will be dropped. The goodness of fit of the models (Full model vs the Reduced model) will be evaluated. A REPEATED statement will be used to control for the repeated measures within a subject. The difference between the IC high dose vs saline, the IC low dose vs saline will be presented in the summary along with the estimates and 95% confidence intervals of the estimates. Effect of a source (treatment, ureter, treatment*ureter interaction in full model) will be determined based on the Score Statistics for Type 3 GEE Analysis.

For the primary endpoint analysis, GEE models will be fitted separately for each comparison, namely IC High dose vs Saline, and IC Low dose vs Saline, and IC High dose vs IC Low dose.

An example of SAS syntax is showing below for this analysis, in which the conspicuity is treated as an ordinal response variable and a proportional odds model is used model the better response compared to the poorer response. Stokes et al. (2000)³ recommended that the null hypothesis of treatment effect would be based on the score statistics for Type 3 GEE analysis, whereas the parameter will be the GEE parameter estimates with the empirical standard error because the Z and the Wald statistic generally produce more liberal p-value than the score statistic.

In this example, the treatment is a binary code; IC High dose=1 and Saline=0. For analysis of IC Low dose vs Saline, IC Low dose=1 and Saline=0; when comparing IC High dose vs IC Low dose, IC High dose=1 and IC Low dose=0.

```

PROC GENMOD DATA=respH descending;
  CLASS USUBJID URETER(ref='Right') TRT (ref='Saline');
  MODEL conspicuity = trt ureter trt*ureter
    /LINK=clogit DIST=mult TYPE3; (Model 1)
  REPEATED subject = Usbjid / type=ind;
  ESTIMATE 'OR: IC vs Saline' trt 1 -1/ exp;
  ods output Estimates=OR1 GEEEmpPEst=est1 Type3=pval1;
  Run;

PROC GENMOD DATA=respH descending;
  CLASS USUBJID URETER(ref='Right') TRT (ref='Saline');
  MODEL conspicuity = trt ureter
    /Link=clogit DIST=mult TYPE3; (Model 2)
  REPEATED SUBJECT = Usbjid / type=ind;
  ESTIMATE 'OR: IC vs Saline' trt 1 -1/ exp;
  ods output Estimates=OR2 GEEEmpPEst=est2 Type3=pval2;
  Run;

```

Where:

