5.1.1. Missing Data Handling Procedure

When conspicuity assessment cannot be performed, conspicuity score will be missing. Reason for each Not Assessed cases will be documented in the database.

- For the primary analysis (Table 14.2.1.1), missing data will not be imputed. Subjects will be included in the input dataset as is. This analysis will be referred to as the Observed Data Analysis.
- However, the impact of missing data will be evaluated by performing 3 sensitivity analyses. The sensitivity analysis will use the same model specified for the primary analysis; nominal p-values from each sensitivity analysis will be reported as. Those 3 sensitivity analyses are described below:
 - Sensitivity Analysis 1 – This analysis will include all MITT subjects who have no missing data. That is, all subjects in this analysis will have 4 conspicuity scores as planned (Table 14.2.1.2).

- Sensitivity Analysis 2 – This analysis will exclude all subjects who are not in the PP population and subjects who have ≥ 1 missing data. This would represent the best outcome for the study since all potential confounded issues will be removed (Table 14.2.1.3).
- Sensitivity Analysis 3 – This analysis will impute the missing data that creates the worst scenario for the study (Table 14.2.1.4).
 - Missing data for Saline Treatment: Assign missing value for saline treatment to be the best value from this patient if scores are available. If no score is available for this patient, then assign the best score of 5 to missing data.
 - Missing score for IC Treatment: Assign missing value for IC treatment to the worst score the patient had if scores are available. If none is available, assign the worst score of ‘1’ to missing data.

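### A ureter repaired between the saline and IC videos can be counted as an IC gain in the primary and responder analyses; the SAP sets such ureters apart only for time to visualization (TTV)

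*SAP*

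**What the plan says.** - **Order (SAP Section 2).** In every case "each subject will first be injected intravenously with 5 mL 0.9% saline" and filmed, and then "The process will be repeated in the same patient for the IC dose". Only the IC dose is randomized, not the order of saline and IC.
- **Scale (Section 2.1.1).** The lowest grade is "1 = No jet observed". It is a recorded score, not a missing one. Grade 3 can be earned by flow or by colour; grades 4 and 5 need strong flow together with colour contrast.
- **TTV (Section 3.8.3.1).** If a ureter has a problem at the start, "this subject will be censored for this analysis regardless if the issue(s) is or is not fixed during the procedure". The sentence stands among the TTV imputation rules, so the analysis it refers to is TTV.
- **Responders (Sections 3.8.2 and 5.3).** "A responder (Yes/No) variable will be derived for each subject by comparing the conspicuity score following IC treatment vs the conspicuity score after saline treatment". A ureter responds if IC minus saline is at least 1 and the IC score is 3 or more. Only missing data remove a ureter.
- **Primary analysis (Section 5.1).** The full model is "MODEL conspicuity = trt ureter trt*ureter"; the reduced model drops the interaction. Nothing identifies a repaired ureter.
- **Missing data (Section 5.1.1).** "For the primary analysis (Table 14.2.1.1), missing data will not be imputed. Subjects will be included in the input dataset as is". The three sensitivity analyses deal with scores that could not be assessed and with per-protocol status.
- **Populations and covariates (Sections 3.3, 4.4, 5.6).** The mITT criteria, the examples of important deviations and the named covariates do not mention ureter problems or their correction.

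**The concern.** The paired design relies on the saline score being a fair control for the same ureter. A repair between the two recordings breaks that: the ureter filmed after IC is no longer in the state in which it was filmed after saline. Because IC is always second, the error is not balanced between treatments. A repair in that window can only help IC.

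The SAP accepts that such ureters occur and that they would distort one efficacy endpoint, TTV. The same ureters enter the primary odds ratio and the responder rate unmarked. The planned cross-checks would not show the problem. Nothing in the SAP tells the blinded central readers that a ureter was repaired. The surgeon-score analysis (Section 5.5.1) uses the same saline-IC contrast, and the interim conditional power (Section 3.2) uses the same reduced model. At stake are a secondary endpoint and the reported odds ratio and, if IC had little effect and repairs were not rare, the error rate of the primary test.

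**Working it through.** **Step 1: follow one ureter through the rules.** Suppose it scores 1 after saline, is repaired, and scores 3 after IC.

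| Rule | Result |
|---|---|
| TTV, 3.8.3.1 | censored |
| Responder, 3.8.2 and 5.3 | 3 - 1 = 2, which is at least 1, and the IC score is 3: responder |
| Primary model, 5.1 | both scores enter as observed |
| Missing data, 5.1.1 | not triggered, since 1 is a score |
| mITT, 3.3 | kept: both injections given, both videos available |
| Per protocol, 3.3 | kept unless the repair is classed as a major deviation |

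**Step 2: numbers per dose.** Section 3.2 gives 116 - 21 = 95 remaining subjects, and half of that is 47.5, matching the stated 47-48 for the interim analysis. The 116 itself cannot be reproduced because its inputs are redacted. With equal allocation (an assumption) there are about 47 subjects per dose, or 47 x 2 = 94 ureters. One repaired ureter adds at most 1/94 = 1.06 points to the per-ureter responder rate.

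**Step 3: false-positive rate with no IC effect.** The score distributions and repair counts are assumptions. Each figure is for one dose against saline at 0.0499, using a clustered score test for the proportional-odds model, without the Hochberg step.

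*Simulation A.* 4000 replicates; scores 1-5 with probabilities 20/40/37/2/1%; k ureters set to 1 after saline and 3 after IC. The columns differ in the share of ureters whose score is redrawn for the second video.

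| k per dose | 30% redrawn | 60% redrawn | all redrawn |
|---|---|---|---|
| 0 | 4.9% | 4.4% | - |
| 2 | 7.6% | 5.6% | - |
| 3 | 10.8% | 8.2% | about 7% |
| 5 | 23.4% | 17.4% | about 11% |

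At k = 1 a re-run of this model gave about 4.5%, so no inflation.

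*Simulation B.* 3000 replicates; scores 1-5 in a normal ureter with probabilities 10/30/40/15/5%; latent within-subject correlation 0.5; a share f of ureters scores 1 after saline and is normal by the IC video; ureter term omitted. The cut-off was 3.843; the exact value is 3.845, which makes no practical difference. Monte Carlo error near 5% is about sqrt(0.05 x 0.95/3000) = 0.4 points.

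| f | ureters of 94 | kept in | left out |
|---|---|---|---|
| 0 | 0 | 4.5% | 4.7% |
| 1% | 0.9 | 4.6% | 4.6% |
| 2% | 1.9 | 5.6% | 5.0% |
| 5% | 4.7 | 10.2% | 5.1% |
| 10% | 9.4 | 27.4% | 5.3% |

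The spurious odds ratio for a score of 3 or more follows directly. A normal ureter reaches 3 with probability 0.60; at f = 5% the saline probability is 0.95 x 0.60 = 0.57, so the odds ratio is (0.60/0.40)/(0.57/0.43) = 1.13. At f = 1%, 2% and 10% it is 1.03, 1.05 and 1.28.

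**Step 4: with a real IC effect.** In simulation B, power is about 1.00 at a true odds ratio of 3 or 10, with or without these ureters. The responder rate rises by f x (p - r), where p is the chance that the IC score is 3 or more and r is the responder rate among unaffected ureters.

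- Odds ratio 3: p = 4.5/5.5 = 0.818, r about 0.507. At f = 5%, 0.05 x 0.311 = 1.6 points; at 10%, 3.1 points. Simulated rates with these ureters kept in: 0.522 and 0.536.
- Odds ratio 10: p = 15/16 = 0.938, r about 0.753. At f = 5%, 0.9 points; at 10%, 1.8 points. Simulated rates: 0.761 and 0.773.

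**The case against.** The strongest objection is that the sequence is inferred. Section 3.8.3.1 says only that a problem may exist at the start and may be corrected. It does not say that the saline video shows no jet, or that the correction falls between the videos. A repair before the saline recording changes neither comparison, and a problem never repaired lowers both scores and works against the responder rate. This stands: the documents establish a gap in the rules, not that the event will happen.

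The full protocol is also not available, only a letter removing the PK sub-study. A conduct rule there might bar intervention between the recordings or class it as a deviation. That cannot be excluded, since the SAP overrides only the protocol's statistical section. If a repair were a major deviation, the per-protocol set and Sensitivity Analysis 2 would remove the subject, but nothing visible says that it is.

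A reader might infer that a repair can produce gains of up to 4 points. The scale does not support this: grades 4 and 5 need colour contrast, which restored flow alone does not supply, so 1 to 3 is the plausible case.

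A reader might also infer that the primary result is unsafe. That does not follow either. The inflated error rates assume that a blue dye has no effect on a scale that rewards colour, and that several ureters per dose are repaired in the critical window. The responder endpoint carries no alpha (Section 3.4).

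**Conclusion.** The point holds as a gap in the analysis rules. The SAP foresees ureters that are corrected during surgery, handles them for TTV, and would credit IC with any gain from a correction made after the saline video starts and before the IC video ends.

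The size depends on a frequency that the documents do not give. At one ureter per dose the error rate is unaffected (about 4.5%); at two it is about 5.6-7.6%; at about five it is about 10-23%, depending on the assumed scores. These figures apply only if IC has no effect. With a large effect the primary conclusion would stand, and the cost is a responder rate about 1-3 points too high at 5-10% corrected ureters. This is worth correcting because it is cheap and concerns a reported secondary endpoint, not because the primary claim is in doubt.

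**What to change.** 1. Record in the eCRF the time of any ureter correction relative to each injection and each video. The documents do not show whether this is already captured.
2. In Sections 3.8.2 and 5.3, treat responder status as not derivable for a ureter corrected between the start of the saline video and the end of the IC video. Its pair then leaves the observed analysis (Table 14.2.3.1) and counts as a non-responder only in the worst-case Table 14.2.3.2. Apply this by ureter, so that the other ureter stays, and state the denominator for the both-ureters row.
3. Add one prespecified sensitivity run of Table 14.2.1.1 without those saline-IC pairs, again keeping the other ureter.
4. Report the number of such ureters by dose.

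Counting these ureters as non-responders in the main responder table is not advised: it would mark down ureters in which IC may have worked and replace an upward bias with a downward one. The primary test is unchanged; the sensitivity run shows whether these ureters matter to it. The change concerns analysis and recording only, not surgical management.

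Cost: one eCRF field, one extra table run, a few sentences in the SAP, and a few ureters lost from the responder rate and the sensitivity run.

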3.8.3.1. Missing Data Imputation Rules for TTV

In order to calculate TTV, the injection start time and time when blue color is adequate visualized in the ureter jet flow must be present. Although the clinical team will make the best effort to eliminate missing or partial time, mistakes could occur. The following rules will be implemented should a subject had missing or partial injection time or time when blue color in the ureter jet flow is adequately visualized.

1. When the injection start time is missing or partial

- 1) If injection start time is missing but the completion time is present, the missing start time will be set to be the same as the injection completion, and vice versa.
- 2) If the hour and minutes are non-missing but the seconds are missing for injection start time, the first second (01) will be assigned to the injection time.
- 3) Otherwise the median elapsed time (defined as time between surgery start time and injection start time) in the study across all subjects who did not have missing data will be used to impute the missing time. That is, the missing injection start time will be set as (Surgery start time + median elapsed time).

The rules will be implemented based on this order.

2. When event occurred but the time is missing or partial

A subject is considered to have had this event when the conspicuity score is 4 or higher per central reader score for this ureter. When a subject has this event but the time when the event occurred is missing, the following rules will be applied.

- 1) If the time is partial (i.e., only the seconds are missing), the first second (01) will be assigned.
- 2) If the time is missing, the subject will not be censored for this endpoint. The missing time, however, will be assigned to 10 minutes after the injection start time.
- 3) This event will be considered as an important protocol deviation. The subject will be excluded from the efficacy PP analysis set. A sensitivity analysis may be performed for the TTV endpoint based on the efficacy PP analysis set.

If a subject had issue(s) with a ureter initially this subject will be censored for this analysis regardless if the issue(s) is or is not fixed during the procedure.

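### The last-resort rule for a missing injection start can put time to visualization (TTV) below 0 or above 10 minutes, and the SAP has no check for this

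*SAP*

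**What the plan says.** SAP Section 3.8.3 defines the endpoint as "TTV (minutes) = (time when adequate visualization occurs - start time of injection) / 60". It limits the window: "TTV event is assessed only after IC treatment within 10 minutes after the injection start". For a ureter without the event, "The censored time will be set to 10 minutes".

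Section 3.8.3.1 gives three ordered rules for a missing or partial injection start:

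1. Completion time present: "the missing start time will be set to be the same as the injection completion, and vice versa".
2. Only the seconds missing: "the first second (01) will be assigned to the injection time".
3. Otherwise: "the missing injection start time will be set as (Surgery start time + median elapsed time"). The median is taken across all subjects without missing data. The rule does not say whether the saline or the IC injection is meant.

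For the event time: "If the time is partial (i.e., only the seconds are missing), the first second (01) will be assigned". If the event time is wholly missing, it is set to 10 minutes after injection start. Missing or partial event times count as an important deviation, exclude the subject from the per-protocol set, and may prompt a sensitivity analysis. That provision stands under event times only, not under imputed starts.

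On the recordings, Section 2 says: "The time period that will be captured on video is from injection to 10 minutes post injection". Section 3.3 makes a video of roughly that length after each treatment a condition of the mITT set, which the TTV table (14.2.4) uses. Section 3.8.3.1 does not name the video as a source for a missing time.

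**The concern.** TTV lives on a 10-minute scale. Rule 3 subtracts a start time guessed from how long other subjects took to get from surgery start to injection. Section 4.2 records surgery duration in hours and lists cystoscopic, robotic, open, laparoscopic and other methods, so a single study-wide median has little prospect of locating one subject's injection to within minutes. A result that is negative or above 10 contradicts the endpoint's own definition, and the SAP does not say what happens to it.

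These values would feed the Kaplan-Meier quartiles and means and, if fitted, the high-versus-low-dose hazard ratio (Section 5.4). Two features spread the damage. Left and right ureters share one injection, so one bad start spoils two observations. Section 5.4 also sets the upper limit of the Kaplan-Meier mean to the largest observed time, so one imputed value above 10 stretches the integration range for its whole group.

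**Working it through.** The documents state no precision, power or error figure for TTV, so there is no figure of the plan's to reproduce. The error of each rule can be worked out directly.

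**Rule 3: surgery start plus median**

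Let *T* be the true TTV, *D* the subject's time from surgery start to IC injection, and *m* the study median of *D*. The event clock time is surgery start + *D* + *T*, and the imputed injection start is surgery start + *m*. So

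imputed TTV = *T* + (*D* − *m*).

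If *D* is taken as normal around *m* with SD σ (an assumption; the documents give no spread),

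P(outside 0–10) = Φ(−*T*/σ) + 1 − Φ((10 − *T*)/σ).

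For *T* = 5 and σ = 5 this is Φ(−1) + 1 − Φ(1) = 0.159 + 0.159 = 0.317.

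| Assumed σ (min) | Below 0, *T* = 5 | Above 10, *T* = 5 | Outside, *T* = 5 | Outside, *T* = 3 or 7 |
|---|---|---|---|---|
| 5 | 15.9% | 15.9% | 32% | 36% |
| 10 | 30.9% | 30.9% | 62% | 62% |
| 15 | 36.9% | 36.9% | 74% | 74% |
| 30 | 43.4% | 43.4% | 87% | 87% |
| 60 | 46.7% | 46.7% | 93% | 93% |

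The mean absolute error is σ√(2/π): 4.0 minutes at σ = 5 and 47.9 minutes at σ = 60. A lognormal check (*T* = 5, median *D* 30 to 90 minutes, log-SD 0.2 to 0.5) gives 40% to 91% outside the window.

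The rule matters only when the event time is present and the start is not. A censored ureter is set to 10 minutes, and a wholly missing event time is set to start + 10, so TTV is 10 in both cases whatever the start.

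**Effect on the Kaplan-Meier mean (illustration on assumed data)**

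Take 48 observations, 5 of them censored at 10 minutes and 43 events with mean 6. The mean is (43 × 6 + 5 × 10)/48 = 6.4. Replace one 6-minute event by an imputed 25. The area to 10 minutes becomes (42 × 6 + 6 × 10)/48 = 6.5. From 10 to 25 minutes the curve stays at 6/48, adding 15 × 6/48 = 1.9. The mean becomes 8.4. With 2 censored instead of 5, it moves from 6.2 to 7.2.

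**Missing seconds set to 01**

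With seconds *s* uniform on 0–59, the clock time moves earlier by *s* − 1. The mean shift is 29.5 − 1 = 28.5 s (0.475 min), with range −1 to +58 s.

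- Only event seconds missing: TTV too short by 28.5 s on average.
- Only start seconds missing: TTV too long by the same amount.
- Both missing: mean bias about zero.

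Impossible values arise only near the ends of the window. With event seconds missing, the chance of a negative TTV is 72%, 47%, 22% and 0% at true TTV of 0.25, 0.5, 0.75 and 1 minute or more. With start seconds missing, the chance of exceeding 10 is 22%, 47% and 72% at 9.25, 9.5 and 9.75 minutes. Assigning second 30 leaves a mean error of 30 − 29.5 = 0.5 s.

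**Missing start set to completion**

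TTV is shortened by exactly the injection duration, which the documents do not give. It is negative if visualization precedes completion.

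**The case against.** The best defence is that rule 3 is a last resort. Start and completion are both to be recorded to the second (Section 3.8.3), and the eCRF holds the exact administration time (Section 4.5), so the rule may never be used. TTV is there to be described (Section 2), lies outside type I error control (Section 3.4), and its hazard ratio is fitted only if the data warrant it (Section 5.4). All of that stands, and it limits the importance of the point. It does not make the rule sound when it is used.

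The spread of *D* is assumed, not documented. That also stands, which is why a range is shown. Even at its favourable end (σ = 5) about a third of imputed values are inadmissible, though about two-thirds are not.

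A reader might infer that the video gives TTV exactly. The documents do not support that. They say recording runs from injection without saying start or completion, describe the length as approximate, and mention no time stamp. When both ureters cannot be seen together, views alternate every 15–30 s, which is of the same order as the 28.5 s error from the seconds rule. The video is an approximate source, but it keeps the error to seconds plus any offset between video start and injection start.

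A reader might also infer that the seconds rule biases TTV in one direction. It does not: the sign depends on which time is partial, and the rule makes no reference to dose. The per-protocol exclusion and optional sensitivity analysis partly answer the complaint about event seconds, but they do not reach imputed starts.

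**Conclusion.** The defect is real but minor. Followed as written, rule 3 can produce TTV values that the endpoint's own definition excludes, and no section of the SAP detects or resolves them. On the stated assumptions (*D* normal around the median, true TTV 5 minutes, SD 5 to 60 minutes), 32% to 93% of the values it imputes are inadmissible. The other two rules are lesser problems: about half a minute in a direction that depends on the record, and one injection duration always towards shorter TTV.

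It would be wrong to conclude that the TTV analysis as a whole is unreliable. The number of affected records is unknown and may be zero, and the primary endpoint does not use these times. The point is worth making because the correction costs very little.

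**What to change.** Amend SAP Section 3.8.3.1 as follows.

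- Delete the rule that adds the median elapsed time to surgery start.
- When the injection start is missing, take TTV as elapsed time on the IC video to adequate visualization for that ureter. Use the same event definition as for all other records, not merely the first appearance of blue, which may come earlier. State who reads the time, and record the 15–30 s resolution when views alternate and any offset between video start and injection start.
- If the video cannot be used, treat a known event as interval-censored between 0 and 10 minutes, or set TTV missing with a sensitivity analysis. Where completion was recorded, event time minus completion is a lower bound on TTV and narrows the interval.
- Assign second 30 rather than 01 to missing seconds.
- Add a validity check: any derived TTV outside 0–10 minutes triggers review of the record. Do not clamp the value to the limit, since that would turn a negative time into an event at time 0.
- Report how many TTV values rest on an imputed or video-derived time, by dose group.

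The cost is SAP wording and a few minutes of video review per affected record, using recordings that mITT membership already requires.
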